8.3.3.3. Assessment of outcomes

The investigator will assess the outcome of all unsolicited AEs (including SAEs) recorded during the study as:

- Recovered/resolved.
- Recovering/resolving.
- Not recovered/ not resolved.
- Recovered with sequelae/resolved with sequelae.
- Fatal (SAEs only).

8.3.3.4. Medically attended visits

For each solicited and unsolicited symptom the subject experiences, the subject will be asked if she received medical attention defined as hospitalisation, or an otherwise unscheduled visit to or from medical personnel for any reason, including emergency room visits. This information will be recorded in the eCRF.

8.4. Reporting of serious adverse events, pregnancies, and other events

8.4.1. Prompt reporting of serious adverse events, pregnancies, and other events to GSK Biologicals

SAEs that occur in the time period defined in Section 8.3 will be reported promptly to GSK within the timeframes described in Table 19, once the investigator determines that the event meets the protocol definition of a SAE.

Pregnancies that occur in the time period defined in Section 8.3 will be reported promptly to GSK within the timeframes described in Table 19, once the investigator becomes aware of the pregnancy.

Table 19 Timeframes for submitting serious adverse event and pregnancy to GSK Biologicals

Type of Event	Initial Reports		Follow-up of Relevant Information on a Previous Report	
	Timeframe	Documents	Timeframe	Documents
SAEs	24 hours*‡	Expedited Adverse Events Report	24 hours*	Expedited Adverse Events Report
Pregnancies	2 weeks*	Electronic pregnancy report	2 weeks*	Electronic pregnancy report

*Timeframe allowed after receipt or awareness of the information.

‡The investigator will be required to confirm review of the SAE causality by ticking the 'reviewed' box in the electronic Expedited Adverse Events Report within 72 hours of submission of the SAE.

8.4.3. Completion and transmission of SAE reports to GSK Biologicals

Once an investigator becomes aware that a SAE has occurred in a study subject, the investigator (or designate) must complete the information in the electronic Expedited Adverse Events Report WITHIN 24 HOURS. The report will always be completed as thoroughly as possible with all available details of the event. Even if the investigator does not have all information regarding a SAE, the report should still be completed within 24 hours. Once additional relevant information is received, the report should be updated WITHIN 24 HOURS.

The investigator will always provide an assessment of causality at the time of the initial report. The investigator will be required to confirm the review of the SAE causality by ticking the 'reviewed' box in the electronic Expedited Adverse Events Report within 72 hours of submission of the SAE.

8.4.3.1. Back-up system in case the electronic reporting system does not work

If the electronic reporting system does not work, the investigator (or designate) must complete, then date and sign a paper Expedited Adverse Events Report and fax it to the Study Contact for Reporting SAEs (refer to the [Sponsor Information](#)) or to GSK Biologicals Clinical Safety and Pharmacovigilance department within 24 hours.

This back-up system should only be used if the electronic reporting system is not working and NOT if the system is slow. As soon as the electronic reporting system is working again, the investigator (or designate) must complete the electronic Expedited Adverse Events Report within 24 hours. The final valid information for regulatory reporting will be the information reported through the electronic SAE reporting system.

8.4.4. Completion and transmission of pregnancy reports to GSK Biologicals

Once the investigator becomes aware that a subject is pregnant, the investigator (or designate) must complete the required information onto the electronic pregnancy report WITHIN 2 WEEKS.

Note: Conventionally, the estimated gestational age (EGA) of a pregnancy is dated from the first day of the last menstrual period (LMP) of the cycle in which a woman conceives. If the LMP is uncertain or unknown, dating of EGA and the estimated date of delivery (EDD) should be estimated by ultrasound examination and recorded in the pregnancy report.

8.4.5. Updating of SAE and pregnancy information after removal of write access to the subject's eCRF

When additional SAE, pregnancy information is received after removal of the write access to the subject's eCRF, new or updated information should be recorded on the appropriate paper report, with all changes signed and dated by the investigator. The updated report should be faxed to the Study Contact for Reporting SAEs (refer to the [Sponsor Information](#)) or to GSK Biologicals Clinical Safety and Pharmacovigilance department within the designated reporting time frames specified in [Table 19](#).

8.4.6. Regulatory reporting requirements for serious adverse events

The investigator will promptly report all SAEs to GSK in accordance with the procedures detailed in Section [8.4.1](#). GSK Biologicals has a legal responsibility to promptly notify, as appropriate, both the local regulatory authority and other regulatory agencies about the safety of a product under clinical investigation. Prompt notification of SAEs by the

investigator to the Study Contact for Reporting SAEs is essential so that legal obligations and ethical responsibilities towards the safety of other subjects are met.

Investigator safety reports are prepared according to the current GSK policy and are forwarded to investigators as necessary. An investigator safety report is prepared for (a) SAE(s) that is/are both attributable to the investigational vaccines and unexpected. The purpose of the report is to fulfil specific regulatory and GCP requirements, regarding the product under investigation.

8.5. Follow-up of adverse events, serious adverse events and pregnancies

8.5.1. Follow-up of adverse events and serious adverse events

8.5.1.1. Follow-up during the study

After the initial AE/SAE report, the investigator is required to proactively follow each subject and provide additional relevant information on the subject's condition to GSK Biologicals (within 24 hours for SAEs; refer to [Table 19](#)).

All SAEs documented at a previous visit/contact and designated as not recovered/not resolved or recovering/resolving will be reviewed at subsequent visits/contacts until the end of the study.

All AEs documented at a previous visit/contact and designated as not recovered/not resolved or recovering/resolving will be reviewed at subsequent visits/contacts until 30 days after the last vaccination.

8.5.1.2. Follow-up after the subject is discharged from the study

The investigator will follow subjects with SAEs or subjects withdrawn from the study as a result of an AE, until the event has resolved, subsided, stabilised, disappeared, or until the event is otherwise explained, or the subject is lost to follow-up.

If the investigator receives additional relevant information on a previously reported SAE, he/she will provide this information to GSK Biologicals using a paper/ electronic Expedited Adverse Events Report and/or pregnancy report as applicable.

GSK Biologicals may request that the investigator performs or arranges the conduct of additional clinical examinations/tests and/or evaluations to elucidate as fully as possible the nature and/or causality of the AE or SAE. The investigator is obliged to assist. If a subject dies during participation in the study or during a recognised follow-up period, GSK Biologicals will be provided with any available post-mortem findings, including histopathology.

8.5.2. Follow-up of pregnancies

Pregnant subjects will be followed to determine the outcome of the pregnancy. At the end of the pregnancy, whether full-term or premature, information on the status of the mother and child will be forwarded to GSK Biologicals using the electronic pregnancy report and the Expedited Adverse Events Report if applicable. Generally, the follow-up period doesn't need to be longer than six to eight weeks after the estimated date of delivery.

Regardless of the reporting period for SAEs for this study, if the pregnancy outcome is a SAE, it should always be reported as SAE.

8.6. Treatment of adverse events

Treatment of any AE is at the sole discretion of the investigator and according to current good medical practice. Any medication administered for the treatment of an AE should be recorded in the subject's eCRF (refer to Section 6.6).

8.7. Unblinding

GSK Biologicals' policy (which incorporates ICH E2A guidance, EU Clinical Trial Directive and US Federal Regulations) is to unblind the report of any SAE which is unexpected and attributable/suspected to be attributable to the investigational vaccines, prior to regulatory reporting. The GSK Biologicals' Central Safety Physician is responsible for unblinding the treatment assignment in accordance with the specified timeframes for expedited reporting of SAEs (refer to Section 8.4.1).

8.8. Emergency unblinding

Unblinding of a subject's individual treatment code should occur only in the case of a medical emergency, or in the event of a serious medical condition, when knowledge of the treatment is essential for the clinical management or welfare of the subject, as judged by the investigator.

The emergency unblinding process consists of the automated system SBIR that allows the investigator to have unrestricted, immediate and direct access to the subject's individual study treatment.

The investigator has the option of contacting a GSK Biologicals' On-call Central Safety Physician (or Backup) if he/she needs medical advice or needs the support of GSK to perform the unblinding (i.e. he/she cannot access SBIR).

Any emergency unblinding must be fully documented by using the Emergency Unblinding Documentation Form, which must be appropriately completed by the investigator and sent within 24 hours to GSK Biologicals.

**GSK Biologicals' Contact information for Emergency Unblinding
24/24 hour and 7/7 day availability**

GSK Biologicals' Central Safety Physician:

+^{PPD} [REDACTED] (GSK Biologicals Central Safety Physician on-call)

GSK Biologicals' Central Safety Physician Back-up:

+^{PPD} [REDACTED]

Emergency Unblinding Documentation Form transmission:

Fax: [REDACTED] or +^{PPD} [REDACTED]

8.9. Subject card

Study subjects must be provided with the address and telephone number of the main contact for information about the clinical study.

The investigator (or designate) must therefore provide a “subject card” to each subject. In an emergency situation this card serves to inform the responsible attending physician that the subject is in a clinical study and that relevant information may be obtained by contacting the investigator. Subjects must be instructed to keep subject cards in their possession at all times.

8.10. Safety monitoring

8.10.1. Safety review team

The SRT includes as core members the GSK Biologicals' Central Safety Physician, the Clinical & Epidemiology Project Lead (CEPL), Epidemiologist, Clinical Regulatory Affairs representative and the Biostatistician of the project. The SRT is responsible for on-going safety monitoring of the entire project and will meet on a regular basis. In order to keep all people involved in the conduct, cleaning and final analysis of the study blinded, the SRT will monitor safety in a **blinded** manner.

In addition to the existing SRT, an unblinded safety evaluation will be performed by an iSRC. The SRT will inform the iSRC about any potential safety concern relevant to the study and vice versa.

8.10.2. Internal safety review committee

Since this will be the first time that the investigational RSV vaccine formulation containing 120 µg of the PreF antigen will be administered in humans, a staggered vaccination and monitoring by an iSRC, authorised by the GSK Biologicals' Vaccine Safety Monitoring Board (VSMB), have been established to ensure maximum safety of the subjects in the study.

The iSRC will include the following GSK personnel: a Safety Physician (Vaccines Clinical Safety & Pharmacovigilance representative [VCSP]), a Clinical Research and

Development Leader (CRDL), and a Biostatistician, external to the study/project and with no conflicts of interest in the outcome of the study. The GSK Safety Physician will act as the Chair of the iSRC. Additionally, the iSRC will have one *ad hoc*, non-voting member: an independent statistician in charge of providing unblinded data to the iSRC.

When the first 25% of the subjects are vaccinated in the study (Step 1), enrolment will be paused until completion of an unblinded iSRC review of all safety data collected up to (minimum) 7 days post-vaccination (including Day 7 haematology and biochemistry parameters).

It was deemed appropriate to place the sample size “cut-off” at the first 25% of subjects vaccinated based on the rate of Grade 3 AEs (solicited and unsolicited) during the 7-day post vaccination period observed in the RSV F-020 study with the non-adjuvanted 60µg PreF formulation, which was approximately 5%.

The table below shows that with 25% of subjects vaccinated (25 subjects per group) we have ~90% chance to observe a given Grade 3 event if the true incidence is 10% (i.e. ~2fold of what we would expect , based on RSV F-020 study data).

Table 20 Probability to observe at least one subject with an event of a given true incidence when looking after 25 enrolled subjects/group

True incidence	N = 25
1%	0.222
2%	0.397
5%	0.723
10%	0.928
15%	0.983
20%	0.996
30%	1

N = subjects per group

During the planned (and any *ad-hoc* iSRC safety evaluations, if applicable), the iSRC will review all available safety data in an **unblinded** manner, while taking into account any other findings that could have an impact on the safety of the subjects, and will determine whether there is a safety signal or not.

If no safety signal is observed during the planned safety evaluation after the first 25% of subjects have been vaccinated (Step 1), the favourable outcome of the safety review will be documented and provided in writing to the RSV study team and investigator(s) and enrolment/vaccination of the remaining subjects (Step 2) can start.

If a safety signal is observed during the planned safety evaluation, the iSRC leader is responsible for urgent communication and escalation of the concern to the GSK Biologicals' VSMB and communication to the study team. The VSMB will then decide during an *ad hoc* meeting whether to suspend, modify or continue the conduct of the study. Already vaccinated subjects will continue all planned visits, including the capture of all safety data. However, further enrolment/vaccination cannot proceed until VSMB review and corresponding outcome is available.

The decision of the GSK Biologicals' VSMB will be documented and provided in writing to the investigator(s). Ethics Committees and Competent Authorities will also be notified, as applicable.

In addition to the planned iSRC evaluation, *ad hoc* iSRC reviews can be organized, if deemed necessary, at any time during the study.

Details about the working of the iSRC will be documented in an iSRC Charter.

In addition to the above, the RSV F-021 iSRC outputs and review outcome will be provided to the Independent Data Monitoring Committee (IDMC) of the RSV F-004 study (first study in which the investigational RSV vaccine will be administered to pregnant women).

9. SUBJECT COMPLETION AND WITHDRAWAL

9.1. Subject completion

A subject who is available for the contact at Day 360 foreseen in the protocol is considered to have completed the study.

9.2. Subject withdrawal

Withdrawals will not be replaced.

9.2.1. Subject withdrawal from the study

From an analysis perspective, a 'withdrawal' from the study refers to any subject who is not available for the contact at Day 360 foreseen in the protocol.

All data collected until the date of withdrawal/last contact of the subject will be used for the analysis.

A subject is considered a 'withdrawal' from the study when no study procedure has occurred, no follow-up has been performed and no further information has been collected for this subject from the date of withdrawal/last contact.

Investigators will make at least 3 documented attempts (e.g. 2 phone calls and a letter sent by certified mail to the last known address) to contact those subjects who do not return for scheduled visits and/or are not available for the contact at Day 360.

Information relative to the withdrawal will be documented in the eCRF. The investigator will document whether the decision to withdraw a subject from the study was made by the subject herself, or by the investigator, as well as which of the following possible reasons was responsible for withdrawal:

- Serious adverse event.
- Non-serious adverse event.

- Protocol violation (specify).
- Consent withdrawal, not due to an adverse event*.
- Moved from the study area.
- Lost to follow-up.
- Other (specify).

*In case a subject is withdrawn from the study because she has withdrawn consent, the investigator will document the reason for withdrawal of consent, if specified by the subject, in the eCRF.

Subjects who are withdrawn from the study because of SAEs/AEs must be clearly distinguished from subjects who are withdrawn for other reasons. Investigators will follow subjects who are withdrawn from the study as result of a SAE/AE until resolution of the event (see Section 8.5.1.2).

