Placebo	Formulation buffer S9b				X

- **Control:** placebo control
- **Vaccination schedule:** One intramuscular vaccination at Day 0.
- **Treatment allocation:** Subjects will be randomised using a centralised randomisation system on internet (SBIR) at Day 0. The randomisation algorithm will use a minimisation procedure accounting for age (18 - 32 years or 33 - 45 years) and centre.
- **Blinding:** Observer-blind in Epoch 001 and single-blind in Epoch 002.

Table 3 Blinding of study epochs

Study Epochs	Blinding
Epoch 001	observer-blind
Epoch 002	single-blind

- **Sampling schedule:**

- **Blood samples for haematology/biochemistry** will be collected (~10 mL) from all subjects at Visit 1 (Day 0), Visit 2 (Day 7), Visit 3 (Day 30), Visit 4 (Day 60) and Visit 5 (Day 90).

- **Blood samples for humoral immune response evaluation** will be collected (~17 mL) from all subjects at Visit 1 (Day 0), Visit 3 (Day 30), Visit 4 (Day 60) and Visit 5 (Day 90).
- **Nasal swabs** will be collected from subjects in case of a MA-RTI from enrolment (Visit 1) until Contact 3.
- **Type of study:** self-contained
- **Data collection:** Electronic Case Report Form (eCRF).
- **Safety monitoring:** When the first 25% of subjects are vaccinated in the study, enrolment will be paused until completion of an unblinded review by a GSK iSRC. Continuation of study enrolment will be conditional to a favourable outcome of the iSRC evaluation of all available safety and reactogenicity data collected up to at least 7 days post-vaccination (including Day 7 haematology and biochemistry parameters). In addition, the blinded safety data will be reviewed by GSK Biologicals' SRT on a regular basis throughout the study.

Refer to Section 8.10 for description of safety monitoring.

- In case of a MA-RTI (e.g. visit to the GP for respiratory symptoms including but not limited to cough, sputum production, difficulty breathing), the subject will be asked to contact the investigator to enable the collection of a nasal swab within 72 hours after the medical attendance.

Refer to Section 5.6.11 for more information on the procedure of nasal swabbing.

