6.6.1. Recording of concomitant medications/products and concomitant vaccinations

The following concomitant medication(s)/product(s)/vaccine(s) must be recorded in the eCRF.

- All concomitant medications/products, except vitamins and dietary supplements, administered as of study vaccination and up to 29 days after vaccination (Day 0 to Day 29).
- Any concomitant vaccination, administered during the study period.
- Prophylactic medication (i.e. medication administered in the absence of ANY symptom and in anticipation of a reaction to the vaccination).

E.g. an anti-pyretic is considered to be prophylactic when it is given in the absence of fever and any other symptom, to prevent fever from occurring [fever is defined as temperature $\geq 37.5^{\circ}\text{C}$ for oral, axillary or tympanic route, or $\geq 38.0^{\circ}\text{C}$ for rectal route].

- Any concomitant medications/products/vaccines listed in Section 6.6.2 during the period specified in that section.
- Any concomitant medications/products/vaccines relevant to a SAE to be reported as per protocol or administered during the study period for the treatment of a SAE. In addition, concomitant medications relevant to SAEs need to be recorded on the expedited Adverse Event report.
- Any prescribed treatment for the MA-RTIs as of study vaccination till end of study.

6.6.2. Concomitant medications/products/vaccines that may lead to the elimination of a subject from ATP analyses

The use of the following concomitant medications/products/vaccines will not require withdrawal of the subject from the study but may determine a subject's evaluability in the ATP analysis. See Section 10.5 for cohorts to be analysed.

- Any investigational or non-registered product (drug or vaccine) other than the study vaccines used during the study period.
- Immunosuppressants or other immune-modifying drugs administered chronically (i.e. more than 14 days in total) or any long-acting immune-modifying drugs (e.g. infliximab) administered any time up to 90 days post-vaccination. For corticosteroids, this will mean $\geq 10\text{mg/day}$, or equivalent. Inhaled and topical steroids are allowed.
- A vaccine not foreseen by the study protocol administered during 30 days following vaccination*, with the exception of seasonal influenza vaccine which may be administered ≥ 15 days after the dose of study vaccine.

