8.1.5. Medically Attended Respiratory Tract Infections

A MA-RTI is defined as a subject's visit to a health care professional (e.g. GP) for any respiratory symptom, including (but not limited to) cough, sputum production and difficulty breathing.

All AEs related to MA-RTIs occurring during the period starting with the administration of study vaccine up to Contact 3 must be recorded in a specific eCRF form for MA-RTI, irrespective of intensity or whether or not they are considered administration-related.

8.2. Events or outcomes not qualifying as adverse events or serious adverse events (pregnancy)

Female subjects who become pregnant after the vaccination may continue the study at the discretion of the investigator.

While pregnancy itself is not considered an AE or SAE, any adverse pregnancy outcome or complication or elective termination of a pregnancy for medical reasons will be recorded and reported as an AE or a SAE.

Note: The pregnancy itself should always be recorded on an electronic pregnancy report.

The following should always be considered as SAE and will be reported as described in Sections 8.4.1 and 8.4.3:

- Spontaneous pregnancy loss, including:
 - spontaneous abortion, (spontaneous pregnancy loss before/at 22 weeks of gestation)
 - ectopic and molar pregnancy
 - stillbirth (intrauterine death of foetus after 22 weeks of gestation).

Note: the 22 weeks cut-off in gestational age is based on WHO-ICD 10 noted in the EMA Guideline on pregnancy exposure [EMA, 2006]. It is recognized that national regulations might be different.

- Any early neonatal death (i.e. death of a live born infant occurring within the first 7 days of life).
- Any congenital anomaly or birth defect (as per [CDC MACDP, 1996] guidelines) identified in the offspring of a study subject (either during pregnancy, at birth or later) regardless of whether the foetus is delivered dead or alive. This includes anomalies identified by prenatal ultrasound, amniocentesis or examination of the products of conception after elective or spontaneous abortion.

Furthermore, any SAE occurring as a result of a post-study pregnancy AND considered by the investigator to be reasonably related to the investigational vaccines will be reported to GSK Biologicals as described in Section 8.4.3. While the investigator is not obligated to actively seek this information from former study participants, he/she may learn of a pregnancy through spontaneous reporting.

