10.6. Derived and transformed data

The study groups will be defined by treatment actually administered.

Demography

- For a given subject and a given demographic variable, missing measurements will not be replaced.

Safety

- For a given subject and the analysis of solicited symptoms during the 7-day follow-up period after vaccination, missing or non-evaluable measurements will not be replaced. Therefore the analysis of the solicited symptoms based on the TVC will include only vaccinated subjects with documented safety data (i.e., symptom screen completed).
- For analysis of unsolicited AEs, SAEs and for the analysis of concomitant medications, all vaccinated subjects will be considered. Subjects who did not report an event or concomitant medication will be considered as subjects without the event or the concomitant medication respectively.

Immunogenicity

- Any missing or non-evaluable immunogenicity measurement will not be replaced:
 - For the within-group assessment, the descriptive analysis performed for each assay at each timepoint will exclude subjects with a missing or non-evaluable measurement.
 - For the between group assessments, the Analysis of covariance (ANCOVA) model will be fitted at each timepoint based on the subjects having a result at both the baseline and the considered timepoint.

- A seronegative subject will be defined as a subject whose antibody titre/concentration is below the cut-off value of the assay. A seropositive subject is a subject whose antibody titre/concentration is greater than or equal to the cut-off value of the assay.
- The geometric mean titres (GMTs)/geometric mean concentrations (GMCs) will be computed by taking the anti-logarithm of the arithmetic mean of the log₁₀ transformed titres/concentrations.
- Vaccine response in terms of RSV neutralising antibodies will be defined as:
 - At least a 4-fold increase from pre-vaccination if pre-vaccination neutralising antibody titre $< 7 \log_2$ (< 128).
 - At least a 3-fold increase from pre-vaccination if pre-vaccination neutralising antibody titre in $[7-8] \log_2$ ($[128-256]$).
 - At least a 2.5-fold increase from pre-vaccination if pre-vaccination neutralising antibody titre in $> 8-10 \log_2$ ($> 256-1024$).
 - At least 1-fold from pre-vaccination if pre-vaccination neutralising antibody titre $> 10 \log_2$ (> 1024).
- The handling of data below the assay LLOQs for GMT/GMC calculations and evaluation of vaccine response will be described in the SAP.

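### After the single dose, an investigator's decision to withdraw a woman for an AE or protocol violation ends general safety follow-up, yet the SAE analysis still counts her as event-free

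*Protocol*

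**What the plan says.** The schedule in Protocol Section 3 is "One intramuscular vaccination at Day 0".

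Section 9.2.1 treats a woman as withdrawn when nothing further is done or collected after her last contact. On who decides, it says: "The investigator will document whether the decision to withdraw a subject from the study was made by the subject herself, or by the investigator". The reasons to be recorded include SAE, "Non-serious adverse event" and protocol violation. On what follows, it says: "Investigators will follow subjects who are withdrawn from the study as result of a SAE/AE until resolution of the event". Section 8.5.1.2 ties follow-up after discharge to the event in the same way. Section 8.3.2 does not oblige investigators to look for later events in former participants.

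Section 10.2 sets any SAE and RSV-associated MA-RTIs as secondary endpoints up to study conclusion. For the SAE analysis, Section 10.6 keeps every vaccinated woman in the denominator: "Subjects who did not report an event or concomitant medication will be considered as subjects without the event".

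Elsewhere the protocol favours retention. Section 6.6.2 says that listed concomitant products "will not require withdrawal of the subject from the study but may determine a subject's evaluability in the ATP analysis". Section 8.10.2 keeps vaccinated women in all planned visits even if the iSRC sees a signal. On pregnancy, Section 8.2 says: "Female subjects who become pregnant after the vaccination may continue the study at the discretion of the investigator".

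**The concern.** In a multi-dose trial, withdrawal for an AE can at least stop further exposure. Here exposure is complete on Day 0, so an investigator's decision to withdraw a woman removes only data. The protocol gives no criteria for that decision. It also does not direct sites to stop individual procedures while keeping the safety contacts.

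Take a woman withdrawn on Day 10 for a non-serious AE. Only that AE is then pursued, but she enters the SAE tabulation as SAE-free to Day 360 although nobody asked. If she was withdrawn for a protocol violation, no follow-up is described at all.

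At stake is the completeness of the secondary safety description in a trial that gives 120 µg to humans for the first time, and whose background sections report a respiratory SAE that the investigator considered related in the preceding study.

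**Working it through.** The plan states no figure for this point, so the main check sets the provisions side by side.

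1. **Exposure.** One dose on Day 0 (Section 3). Nothing is left to withhold afterwards.
2. **Who may end follow-up.** The woman or the investigator (9.2.1), with SAE, non-serious AE and protocol violation among the codes.
3. **What continues.** After AE or SAE: the causing event, to resolution (9.2.1, 8.5.1.2). After a protocol violation: nothing specified. Other later SAEs: not sought, though one that the investigator learns of and considers related is notified (8.3.2). MA-RTIs: no provision after withdrawal.
4. **What the endpoints need.** SAEs and RSV-associated MA-RTIs to study conclusion (10.2).
5. **How silence is scored.** No reported SAE counts as no SAE, with all vaccinated women in the denominator (10.6).

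Steps 3 to 5 do not fit together: data collection can end early, the endpoint period does not, and the missing time is scored as event-free. The error has one direction, because an uncollected SAE can lower the observed rate but never raise it. A woman withdrawn because of an SAE already counts as a case. The proportion with any SAE is therefore affected only by women withdrawn without one.

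**Illustration of size.** All inputs are assumptions; the protocol gives no withdrawal rate, SAE rate or risk ratio. Per 100 vaccinated women, let w be withdrawn soon after vaccination without a reported SAE, p the later SAE risk, and RR the risk ratio in the withdrawn women.

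- Observed rate = (100 − w)·p / 100
- True rate = [(100 − w)·p + w·p·RR] / 100
- Lost SAEs per group = w·p·RR
- Relative understatement = w·RR / [(100 − w) + w·RR]; p cancels

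| w | p | RR | True | Observed | Lost SAEs | Relative understatement |
|---|---|---|---|---|---|---|
| 1 | 1% | 1 | 1.00% | 0.99% | 0.01 | 1/100 = 1.0% |
| 2 | 2% | 2 | 2.04% | 1.96% | 0.08 | 4/102 = 3.9% |
| 5 | 2% | 5 | 2.40% | 1.90% | 0.50 | 25/120 = 20.8% |
| 5 | 5% | 5 | 6.00% | 4.75% | 1.25 | 25/120 = 20.8% |

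The 95 evaluable of 100 enrolled per group in Section 10.4 is an allowance for evaluability. It is not a forecast of AE withdrawals and is not used as one here.

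**The case against.** The best defence is that Section 9.2.1 is a documentation list, not a withdrawal rule. No event triggers withdrawal, and the AE codes also serve women who leave by their own choice because of an event. Under Section 9.1 a woman reached at Day 360 has completed the study, so one who stops blood draws but takes the calls is already a completer. Section 8.3.1 sets SAE collection to Day 360 for each subject, Section 5.6.18 asks about SAEs at each remote contact, and women who miss visits get at least three contact attempts. All of this is correct. It shows that the sponsor wants retention and that the remedy fits the existing structure. It does not close the gap, because 9.2.1 still recognises an investigator's decision to end all collection, without criteria, and does not carry the retention principle through to the individual woman.

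Four stronger readings are tempting and are not supported.

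- *Pregnancy is a ground for withdrawal.* It is not among the listed reasons. Section 8.2 only leaves continuation to the investigator's discretion, and Section 8.5.2 follows the pregnancy to its outcome and reports any outcome that is an SAE.
- *The women lost are those most likely to have later events.* That is plausible after an AE, but the protocol has no data on it, and nothing suggests it for protocol violations.
- *Day 360 group comparisons are biased towards no difference.* The between-group safety comparisons in Section 10.9 cover the 7-day period only; SAEs over the whole study are described. The copy at hand lacks the text of Section 10.11, so nothing is concluded about MA-RTI denominators.
- *Section 9.2.1 contradicts Section 6.6.2.* Section 6.6.2 says withdrawal is not required, and 9.2.1 does not require it either. The two differ in spirit, not in rule.

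**Conclusion.** The point holds as a gap in the follow-up rules for secondary safety data. Withdrawal decided by the investigator after the only dose can end SAE and MA-RTI collection, while the endpoints run on and unreported SAEs are scored as absent. The effect on descriptive SAE rates is downward only.

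Its size cannot be derived from the protocol. Over the assumed ranges (1 to 5 early withdrawals per 100, later SAE risk 1% to 5%, risk ratio 1 to 5), the loss is 0.01 to 1.25 SAEs per group, a relative understatement of 1% to 21%. The upper end needs the most unfavourable assumptions together, so the effect is probably small. With about 100 women per group, however, even one missed SAE could change how a group is described.

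The primary ranking uses Day 7 safety and Day 30 immunogenicity and is essentially unaffected; no sample size changes.

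**What to change.** In Section 9.2.1, state that after vaccination only the woman's own withdrawal of consent, loss to follow-up or death ends data collection. Handle protocol violations in the analysis through exclusion from the ATP cohort (Section 10.5.2). Where visits or procedures such as blood draws stop for any other reason, keep SAE, pregnancy and MA-RTI collection at the Day 180, 270 and 360 contacts. The reason codes can stay, to record why a woman herself chose to leave.

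In Section 8.2, clarify that this remote safety data collection also continues for women who become pregnant unless they withdraw consent. Their clinical management stays with the investigator.

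The cost is two paragraphs in an amendment and a few telephone contacts that are already scheduled; there are no new procedures. One limit remains: a contact can capture an MA-RTI, but confirming RSV still needs the swab. The site or home collection in Section 5.6.11 can provide it if the woman agrees.
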